EFFECT OF TOPICAL INTRA-AURICULAR LIDOCAINE ON TINNITUS: A RANDOMIZED DOUBLE-BLIND PLACEBO-CONTROLLED STUDY. NCT05711641

AUGUST 04, 2022

STUDY PROTOCOL AND STATISTICAL ANALYSIS PLAN:

Tinnitus is a prevalent symptom, which can drastically impact the quality of life of the individual and for which there is still no proven effective treatment. Lidocaine has been widely investigated with high rates of tinnitus suppression, but its systemic use has not been shown to be viable due to the fleeting response and the risk of potentially serious side effects. The clinical observation of the improvement of chronic tinnitus in some individuals after the use of otological drops indicated for the treatment of otitis externa aroused our interest in the action of topical intraauricular lidocaine in reducing the intensity of tinnitus, motivating the realization of this study.

The objective of this study is to evaluate the action of 10% topical intraauricular lidocaine on the perception of tinnitus intensity compared to placebo.

This project was designed as a randomized, crossover, placebo-controlled, double-blind, randomized clinical trial. It was approved by the Research Ethics Committee (REC) of the host institution under opinions number 4.188.11 and 5.562.868, and was registered at ClinicalTrial.gov under identification number NCT05711641. The participants were properly informed and signed a informed consent form.

The selected subjects were patients of an otolaryngology center who sought care for tinnitus complaints between April 7, 2021, to April 6, 2022. Of them, 113 patients met the inclusion criteria, and none of the exclusion criteria, and were invited to participate in the study through WhatsApp contact. Thirty-three patients responded and attended the initial appointment, one was excluded for having only pulsatile tinnitus on the day of the appointment. Thirty two patients were enrolled and 28 completed both assessments.

The inclusion criteria were age over 18 years, continuous tinnitus for at least six months, and a visual analog scale (VAS) tinnitus intensity score of at least three points on the days the substances were administered. The exclusion criteria were otologic infection, tympanic membrane perforation, anatomic external ear changes, pulsatile tinnitus, objective tinnitus, known allergy to lidocaine or other topical anesthetics, pregnancy, cardiac arrhythmia, epilepsy, previous history of seizure, or use of anticonvulsants.

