The website www.randomization.com was used to define the order of substance administration, defining whether the patient would start the study as a case or a control. The subjects were randomized by the "Heads or Tails" method in cases of bilateral and symmetrical tinnitus, with one Real coin (official currency of the country) being tossed by the patient himself. "Heads" was previously defined as the right ear, and "tails" as the left ear. In the case of bilateral and asymmetrical tinnitus, the study ear was the ear where the tinnitus was perceived with greater intensity.

The subjects were evaluated regarding the action of intra-auricular topical lidocaine on tinnitus intensity compared to a placebo. The study ear was defined in the first evaluation, the order of substance administration was randomized, and the patients had their medical history researched and underwent physical examination with somatosensory tinnitus analysis and audiological evaluation.

Tinnitus intensity in each ear was measured by the VAS, which ranged from 0–10 points, immediately before each administration and immediately after the substances were removed. The VAS was also used to evaluate somatic maneuvers to determine tinnitus modulation, considered positive in the case of a VAS score variation in at least one of the maneuvers.

An audiological evaluation was carried out in an acoustically treated booth, with TDH 39 and HD 200 headphones, using the MADSEN Itera II audiometer. The tonal threshold between 250–16 kHz was researched by an ascending and descending technique. A tonal threshold up to 8 kHz was classified according to the criteria by Lloyd and Kaplan. The audiometric threshold of high frequencies (9–6 kHz) was measured to determine the tinnitus pitch in these frequency ranges.

The psychoacoustic measures used for analysis in this study were the tinnitus loudness and the minimum masking level (MML), measured in decibel sensation level (dBSL) and performed before and after the application of each of the substances. The pitch was assessed by pure tone sound stimuli or narrow band (NB) noise, being measured in Hz.

Tinnitus loudness was analyzed by presenting the sound most similar to the patient's tinnitus, determined by the pitch, in the ipsilateral ear in cases of unilateral tinnitus or the ear with better hearing in cases of bilateral tinnitus, increasing the intensity by 1 dB until finding the volume closest to the patient's tinnitus.

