The MML was assessed by an NB sound presented to the ipsilateral ear. Starting from the patient's threshold detected for this type of sound, the volume was increased by 1 dB every four seconds until the presented sound masked the tinnitus.

The substances used were 10% lidocaine (active substance) or distilled water (placebo). They were produced in the same compounding pharmacy, being replaced by new ones every 90 days and being stored in identical bottles identified as: "Substance 1" and "Substance 2."

The patient was positioned in a lateral decubitus position, with the tested ear facing up, and 20 drops of the randomized substance were administered and remained in the external acoustic meatus (EAM) for five minutes at each treatment session. For medication removal, the patient was instructed to sit with their head tilted to the side of the study ear, the substance was removed by gravity, and the ear was dried with gauze.

Each ear was its own control and crossover administration was two weeks apart.

Data analysis:

The mean VAS, tinnitus loudness, and MML were compared between lidocaine and the placebo before and after the administration of each substance to evaluate the effect of lidocaine on tinnitus.

To investigate whether any characteristics of the sample correlated with tinnitus variation after the administration of the substances, we compared the VAS, tinnitus loudness, and MML variations related to the variables sex, bruxism/ temporomandibular disorder (TMD), cervical changes, somatosensory tinnitus, modulation, and hearing loss.

Statistical analysis:

Qualitative characteristics of patients and tinnitus were described using absolute and relative frequencies, and quantitative characteristics were described using summary measures (mean, standard deviation, median, minimum, and maximum value). VAS, tinnitus loudness, MML, and variations for each administration were described using summary measures, and the variations between substances were compared using Generalized Estimating Equations (GEE) with marginal normal distribution and identity link function, assuming an interchangeable correlation matrix between substances.

The analyses were performed using the IBM-SPSS for Windows version 22.0 software and tabulated using the Microsoft Excel 2010 software. Statistical significance was set at 5%.

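### The GEE comparison at 5% states no small-sample correction or t reference, with only 28 of 32 patients completing both assessments; a minor, conditional inflation of the error rate

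*Combined protocol and SAP*

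**What the plan says.** The trial is a two-period crossover in which "the order of substance administration was randomized". The administration paragraph adds: "Each ear was its own control and crossover administration was two weeks apart". On numbers, the participant paragraph says "Thirty two patients were enrolled and 28 completed both assessments".

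The Data analysis section names three outcomes: "The mean VAS, tinnitus loudness, and MML were compared between lidocaine and the placebo". Under Statistical analysis, the variations for each administration were "compared using Generalized Estimating Equations (GEE) with marginal normal distribution and identity link function, assuming an interchangeable correlation matrix between substances". The significance level is 5%, with sidedness not given. On software: "The analyses were performed using the IBM-SPSS for Windows version 22.0 software".

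The marginal distribution, link, working correlation, software and level are therefore fixed. Five things are not stated: the test (Wald or score), the variance (robust or model-based), the reference distribution, any small-sample correction, and whether the model used only the 28 completers or also any single visits from the other 4 patients.

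**The concern.** GEE inference is justified when the number of clusters is large. Here the clusters are patients, about 28 of them with two observations each. At that size the unstated choices affect the actual error rate. The usual sandwich variance is biased downward in small samples, and a normal or chi-square cut-off ignores the uncertainty in the estimated variance. Both push a Wald test above its nominal level and make its interval too short.

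At stake is a borderline result on VAS, loudness or MML. It could be called significant at 5% when the same data on a t reference would not support that. The estimated lidocaine-placebo difference does not change.

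**Working it through.** **Inputs.** Nominal level 0.05 (Statistical analysis; two-sided assumed). n = 28 complete pairs (participant paragraph; use of only these pairs is assumed). One variation per patient per substance (administration paragraph). Differences taken as normal, with intercept and substance as the only terms. The plan gives no sample size or power calculation to reproduce; 5% is a set level.

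**Step 1: what the robust Wald test reduces to.** With complete pairs, the GEE estimate is the mean paired difference, d̄. The uncorrected sandwich variance is Σ(dᵢ − d̄)²/n², whatever the exchangeable correlation. Hence

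z = t × √(n/(n−1)), where t is the paired t statistic on n−1 df.

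A fitted exchangeable GEE matched this in 3 of 3 simulated datasets (for example 2.3285 by both routes).

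**Step 2: actual size at a nominal 5%, n = 28.**
- Robust Wald: P(|t₂₇| > 1.96 × √(27/28)) = 0.0649. One million simulated datasets gave 0.0649.
- n−1 variance with a normal cut-off: P(|t₂₇| > 1.96) = 0.0604.
- Generalized score: n·t²/(n−1+t²) > 3.84 requires |t₂₇| > 2.072, so the size is 0.0479.
- Paired t on 27 df (cut-off 2.052): 0.05 under normality.

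**Step 3: sensitivity to the analysis set.** If all 32 had been complete pairs, the first two figures would be 0.0629 and 0.0590. With 28 pairs plus 4 single visits (assumed), a simulation of the fitted GEE with the robust Wald test gave 6.6% (2,500 runs, Monte Carlo SE about 0.5 points). The analysis set matters little to the size of the effect.

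**Step 4: which results would be affected.** The t₂₇ cut-off of 2.052 corresponds to a reported Wald p of 0.0367 (robust) or 0.0402 (n−1 variance). Only p-values between those limits and 0.050 would change side. For example, a robust p of 0.045 has z = 2.005, so t = 2.005/√(28/27) = 1.969, and p = 0.059 on 27 df.

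**Step 5: intervals.** The t interval relative to the Wald interval is 2.052/1.960 = 1.047 times as wide (n−1 variance), or 1.047 × √(28/27) = 1.066 times as wide (robust). The t interval is thus 4.7% to 6.6% wider.

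**The case against.** The strongest reply is that nothing in the documents shows an uncorrected Wald test was used. Naming the software does not settle it, because the procedure options are not given. A generalized score test would be slightly conservative. This stands: the demonstrated fact is the omission, and the 6.0% to 6.5% describes one family of choices that the text permits.

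It can also be said that the effect is small and that the documents report no p-values, so no result is known to fall in the affected band. That stands too, and limits the point to a minor one. Nor is exactness on offer from the alternative. In an illustrative simulation of integer VAS changes with many zeros, the paired t test ran at 4.2% to 5.0% and the robust Wald test at 6.0% to 6.4%. The direction holds, but an exact 5% needs normal differences.

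Several stronger readings are tempting and are not supported:
- *That the trial's error rate was inflated.* This needs the unnamed test to have been an uncorrected Wald test.
- *That the analysis used only the 28 pairs.* The text gives the number of completers, not the analysis set.
- *That GEE is wrong for this design.* An exchangeable correlation does account for the pairing; only the small-sample inference is in question.
- *That a model-based variance could be far worse.* With matching divisors for scale and correlation, the model-based Wald test runs at 6.0% to 6.5% at every correlation examined. Larger departures need mismatched divisors and a high assumed correlation, and the documents give neither.
- *That the missing period term or the three outcomes enlarge this problem.* Period adjustment and multiplicity are separate questions.

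**Conclusion.** The concern holds in limited form. The plan applies a large-sample method to about 28 independent units and states neither a small-sample correction nor a t reference, so the actual level of its tests cannot be determined from the text. If the test was an uncorrected Wald test, the error is 1.0 to 1.5 percentage points above nominal per outcome (6.0% or 6.5% against 5%), and nominal 95% intervals cover about 94.0% or 93.5%.

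These figures assume a two-sided test, normal paired differences, complete pairs and no term beyond substance. The finding is more than a missing detail, because a better method is available at almost no cost. It is still minor: the inflation is conditional and modest, and it matters only for a result already close to the threshold.

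**What to change.** State the test, variance estimator, reference distribution and analysis set actually used. Then, for VAS, loudness and MML, take one of these routes:

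- **Complete pairs.** Base the test and 95% interval on each patient's difference in variation (lidocaine minus placebo), with a t reference on 27 df for 28 pairs. If period is to be adjusted for, regress that difference on sequence coded +1/−1; the intercept is the substance effect, on 26 df.
- **Keep GEE.** Use a small-sample-corrected variance with a t reference.
- **Single-visit patients included.** Use the corrected GEE, or a mixed model with patient as random effect and Satterthwaite df.

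The document is written in the past tense with completers already counted, so this should be reported as a disclosed re-analysis or sensitivity analysis. It needs no new data. Relative to an uncorrected Wald fit without a period term, p-values rise slightly and intervals widen by about 5% to 7%; adjusting for period costs one further df. The change addresses the level of each test only and does nothing about testing three outcomes.

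### No lead outcome is designated among VAS, loudness and MML at one unadjusted 5% level, and the comparisons across six characteristics have no stated model and cannot show who responds to lidocaine

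*Combined protocol and SAP*

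**What the plan says.** Three statements in the combined protocol and SAP matter here.

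- **Efficacy.** Under Data analysis: "The mean VAS, tinnitus loudness, and MML were compared between lidocaine and the placebo before and after the administration of each substance". The stated purpose covers all three measures at once: "before and after the administration of each substance to evaluate the effect of lidocaine on tinnitus". None is called primary or secondary, and no testing order or adjustment is given.
- **Characteristics.** The next paragraph of Data analysis opens "To investigate whether any characteristics of the sample correlated with tinnitus variation after the administration of the substances" and continues "we compared the VAS, tinnitus loudness, and MML variations related to the variables sex", followed by five more variables: bruxism/TMD, cervical changes, somatosensory tinnitus, modulation and hearing loss.
- **Model and level.** Under Statistical analysis, "the variations between substances were compared using Generalized Estimating Equations (GEE", with a normal distribution, identity link and exchangeable correlation. The variance estimator is not stated. The section ends "Statistical significance was set at 5" per cent.

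Other parts of the document lean towards VAS. The objective is perceived tinnitus intensity, eligibility requires a VAS score of at least 3, and "Tinnitus intensity in each ear was measured by the VAS". VAS also has a second use: "The VAS was also used to evaluate somatic maneuvers to determine tinnitus modulation". Loudness and MML are introduced separately as the psychoacoustic measures for analysis.

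**The concern.** With three outcomes sharing one purpose and one unadjusted level, a significant result on any of them could be presented as the effect of lidocaine. Nothing in the text rules that out. VAS is also recorded in each ear, and the analysis text does not say which ear's value is analysed.

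The characteristic analysis raises two further problems. It involves many comparisons with no model and no exploratory label. It also asks about change after the substances, in the plural. A subgroup that changes more on both lidocaine and placebo would show up as a difference, and a reader could take it as a lidocaine response. Only a substance-by-characteristic interaction can separate the two, and none is described.

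**Working it through.** The plan gives no sample size calculation, familywise rate, SD or correlation, so there is no stated figure to reproduce. Inputs from the document: 5% level, 3 outcomes, 6 characteristics (bruxism/TMD counted once), 28 completers of 32 enrolled. Assumed: two-sided tests, all correlations, and subgroup splits.

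**1. Efficacy, any of three outcomes.** If independent, 1 − 0.95³ = 0.143. For correlated outcomes the rate was simulated with normal tests at exactly 5%. The last column uses uncorrected robust errors with a normal reference at n = 28.

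| Outcome correlation | Nominal 5% tests | Uncorrected robust errors |
|---|---|---|
| 0 | 14.3% | 18.2% |
| 0.5 | 12.5% | about 16% |
| 0.7 | 10.9% | about 14% |
| 0.9 | 8.3% | about 10.7% |

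The last column starts from the rate for a single test. The uncorrected variance divides by n instead of n − 1, so the test rejects when |t| on 27 df exceeds 1.96 × √(27/28) = 1.925. That has probability 0.065. For three independent tests, 1 − (1 − 0.0649)³ = 0.182.

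**2. Effect of adjusting.** Bonferroni gives 0.05/3 = 0.0167 per test. If independent, 1 − (1 − 0.0167)³ = 0.049. With t tests at n = 28 the rate is about 4.0% at correlation 0.7 and 3.0% at 0.9. Holm starts from the same threshold.

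**3. Characteristics.** 3 × 6 = 18 comparisons, or 36 if done separately for each substance. If all 18 are independent and tested at 5%, 1 − 0.95¹⁸ = 0.603. With assumed correlations (between outcomes / between characteristics), simulation gives about 0.48 at 0.5/0.4, 0.35 at 0.9/0.4, 0.33 at 0.7/0.7 and 0.26 at 0.9/0.7.

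**4. What the characteristic question can answer.** Suppose a subgroup changes 0.5 to 1.0 SD more on both substances. Comparing post-lidocaine variation alone then detects the difference in 25–72% of trials at a 14/14 split and 14–43% at 4/24. These are true detections of a general difference. They would be wrong only if reported as a response to lidocaine.

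**5. Choosing an interaction test.** False-positive rates at n = 28, no period effect assumed:

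| Split | Pooled t on within-patient differences | GEE, uncorrected robust | GEE, bias-corrected robust |
|---|---|---|---|
| 14/14 | 5% | 7% | 5% |
| 8/20 | 5% | 8% | 6% |
| 5/23 | 5% | 12% | 7% |
| 4/24 | 5% | 14% | 8% |

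These rates guide the remedy. They are not a measure of error in the plan, which specifies no interaction model.

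**6. Precision of the interaction.** With within-person correlation 0.5, a within-patient difference has SD √(2 × (1 − 0.5)) = 1 SD of a single variation. The 95% half-width is 2.056 × √(1/n₁ + 1/n₂): about 0.78 SD at 14/14, 0.86 at 8/20 and 1.11 at 4/24.

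**The case against.** The strongest reply is that VAS is the lead measure in all but name: the objective concerns intensity, VAS measures intensity, and entry depends on VAS. Much of this stands. What is missing is a designation, and the inflation arises only if loudness or MML may carry the claim alone. The document also cites a trial registration that is not available here, so a reader who infers that the trial never had a primary outcome goes further than the text allows.

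Second, the 5% sentence is generic. The plan says the variations were compared across characteristics; it does not say 18 tests were run at 5%. That is a reasonable inference, but still an inference, and the opening phrase of that paragraph leans exploratory.

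Third, a subgroup that changes more on both substances correctly answers the question as worded. This also stands: asking for an interaction changes the question. The change is worthwhile because the trial is about lidocaine, and the present question cannot show who responds to it.

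Fourth, data collection had ended when this text was written, since it reports completers. Naming a lead now cannot restore prespecified error control. This is correct, and the fix therefore needs a route that does not depend on choosing a lead after the fact.

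**Conclusion.** The point holds as a gap in specification that should be fixed. It does not invalidate the trial, and the lidocaine–placebo contrast on VAS remains interpretable.

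The efficacy error rate is about 8–14% instead of 5%, on two conditions: any of the three outcomes may carry the claim, and each test truly runs at 5%. With uncorrected robust errors the range is about 11–18%, and the one-outcome benchmark is itself 6.5%. For the characteristics, the 26–60% range rests on testing each comparison at 5% and on assumed correlations.

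Two stronger readings are not supported. A reader might attach the 26–60% figure to the main conclusion, but it concerns only the characteristic findings. A reader might also take the 25–72% detection rates as false positives, but they are real differences between subgroups.

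Confidence is high on what the text omits. It is lower on the magnitudes, because the documents supply none of the correlations or splits.

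**What to change.** 1. If a record made before the data were seen named study-ear VAS variation as the lead outcome, cite it and test VAS alone at 5%, with loudness and MML secondary and unable to support a positive claim on their own. Otherwise apply Holm or Bonferroni across the three outcomes (smallest p against 0.0167), and label any later choice of VAS as post hoc.
2. Use a t reference or a small-sample-corrected variance for the lidocaine–placebo comparison as well as for the interactions. Without this, naming one outcome may still leave about 6.5%.
3. Assess the six characteristics by comparing within-patient lidocaine-minus-placebo differences between subgroups. Report estimates with 95% CIs and label them exploratory. The t comparison is safer than the corrected GEE when a subgroup is small.

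The cost is wording, one disclosure and a re-analysis of data already collected. Holm or Bonferroni loses some power. Interaction intervals will be wide, about 0.8–1.1 SD either side under the assumed correlation. The pooled t comparison assumes similar variances in the two subgroups. It also drops any of the four non-completers (32 − 28) who have data from only one period, whom the GEE could keep.
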